Most studies examining dairy-dependent vasoprotection have focused on its anti-hypertensive activities with limited regard for other mechanisms that could improve VEF. While important, and as we discuss,¹² blood pressure-lowering activities of dairy are unlikely to fully explain its role in reducing CVD risk. Thus, expected findings from the proposed randomized controlled, cross-over trials are anticipated to be paradigm-shifting by mechanistically linking improvements in VEF by dairy milk, and its protein and lipid fractions, to reductions in PPH-induced oxidative stress responses that otherwise limit NO[•] bioavailability and increase CVD risk. Findings of this application are also expected to provide the first evidence attributing the relative vasoprotective activities of whey protein, casein, and dairy fat on PPH-induced vascular dysfunction in association with improvements in oxidative stress and NO[•] homeostasis. These collective findings are also directly translatable into evidenced-based recommendations supporting forthcoming revisions to the US Dietary Guidelines regarding dairy consumption.

Pitfalls and Alternatives

Based on our preliminary studies, we do not anticipate any conceptual or technical difficulties in this application.

III. Procedures Study Design

This IRB protocol addresses three objectives by completing two separate randomized cross-over studies in two separate cohorts of participants. For clarity, *Study 1* is a 4-arm cross-over study that addresses the work under *Objectives 1 and 2* and will utilize one cohort of participants. *Study 2* is a separate 3-arm cross-over study that addresses the work under *Objective 3* and will utilize a different cohort of participants. Each study aims to enroll 24 participants for a total of 48 participants for all of the anticipated work.

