Studies under Objectives 1 and 2 will be accomplished through a common 4-arm crossover study. For **Objective 1**, which will examine the inhibition of non-fat milk on PPH-induced vascular dysfunction, prediabetic men and women ($n = 24$) in the fasted state will ingest 75 g glucose dissolved in water or nonfat milk (2 cups; 473 mL) on two occasions separated by ≥ 7 d. We will then assess FMD and collect blood samples prior to and at 30 min intervals for 3 h following test beverage ingestion to examine VEF and biomarkers regulating NO[•] bioavailability. In **Objective 2**, which will define independent contributions of dairy proteins in regulating VEF, participants will ingest glucose (75 g) with isonitrogenous quantities of whey protein isolate or sodium caseinate (16.5 g in 473 mL water) on two occasions separated by ≥ 7 d. Identical to Objective 1, FMD and blood samples will be obtained at 30 min intervals for 3 h. For **Objective 3**, which will define vasoprotective activities of dairy fat, a separate cohort of prediabetic men and women ($n = 24$) will complete a 3-arm cross-over study by ingesting glucose (75 g), or glucose with non-fat milk or whole milk (2 cups; 473 mL) on three occasions separated by ≥ 7 d. Identical to Objectives 1-2, FMD and blood samples will be obtained at 30 min intervals for 3 h.

Sampling Criteria and Methods

Enrollment Criteria. Prediabetic men and women are an ideal study population because of their underlying vascular dysfunction and exacerbated PPH.⁸² They will be required to meet these **inclusion criteria**: a) prediabetes (fasting glucose 100-125 mg/dL and hemoglobin A1c 5.7-6.4%⁸³), b) 18-50 y of age, c) non-dietary supplement user, c) no medications affecting vasodilation, inflammation, or energy metabolism, e) no CVD, and f) nonsmoker. To improve homogeneity, we will only enroll individuals having blood pressure $<140/90$ mmHg and total cholesterol <240 mg/dL. Those having any of these **exclusion criteria** will not be enrolled: a) unstable weight (± 2 kg), b) vegetarian or dairy allergy, c) alcohol intake >3 drinks/d or >10 drinks/wk, d) ≥ 7 h/wk of aerobic activity, or e) women who are pregnant, lactating, or have initiated or changed birth control in the past 3-mo. For all studies, the washout period will be 7 d for men and 1 mo for women because women require vascular testing at the same time during their menstrual cycle to account for known changes in vascular reactivity.⁸⁴

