
Power Calculation and Statistics. A power calculation was performed to determine the fewest participants needed to complete the two separate proposed cross-over studies (i.e. *Objectives 1-2* and *Objective 3*). We used FMD data from our studies^{9, 10} and predicted that non-fat milk will protect against PPH-mediated decreases in FMD. Assuming no gender differences, which is consistent with our earlier studies in this area,⁸ 11 prediabetic adults are needed to reject the null hypothesis with 80% power ($P<0.05$). Thus, 24 male and female prediabetics will be enrolled to improve statistical power to >90% while also accounting for study attrition that may occur due to women requiring a longer washout period between trials (1 mo vs. 7 d). Although participants will complete all arms of each cross-over study, statistical analysis will be handled discretely to examine differences between trials within each *Objective*. Baseline comparisons between trials will be performed a paired t-test (*Objectives 1-2*) or 1-way RM ANOVA (*Objective 3*) to ensure no changes in participant health status. Other analyses will be performed by 2-way RM ANOVA to define time and treatment effects, and their interaction. In the presence of any significant effects, Bonferroni's post-test will be used to examine pair-wise differences. To better define postprandial responses between treatments, area under the curve ($AUC_{0-3\text{ h}}$) will be calculated for each biomarker to enable more sensitive comparisons of postprandial responses between treatments and simplify analyses to a paired t-test (*Objectives 1-2*) or 1-way ANOVA (*Objective 3*) as we described.^{9, 10} Lastly, to define correlations between study variables, we will perform multiple linear regression, controlling for within-subject repeated measures.⁸⁵

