Justification of Test Meals. In *Objective 1*, beverages will consist of 75 g glucose in 473 mL water vs. 75 g glucose in 473 mL non-fat milk. This volume of milk was chosen to be consistent with our work⁸ and recommendations of the US Dietary Guidelines for Americans. The amount of glucose administered (75 g) is equivalent to that of a standard oral glucose challenge. We fully acknowledge that test beverages in *Objective 1* are not isocaloric. While this might be viewed as a limitation, this approach is being specifically undertaken to determine the vasoprotective effects of non-milk mediated through an attenuation of PPH-dependent vascular dysfunction rather than through the displacement of carbohydrate. In *Objective 2*, protein is being administered at 16.5 g to reflect total protein of non-fat milk, rather than their proportional contributions in milk, to pharmacologically define each protein in regulating VEF. In *Objective 3*, beverages will consist of glucose (75 g; positive control) vs. glucose (75 g) ingested with non-fat milk or whole milk. Despite associations between dietary fat and CVD risk, experimental evidence is lacking to support: 1) widespread restrictions of fat-containing dairy foods, and 2) that dairy fat, which is predominately saturated fat, is causatively responsible for increasing CVD risk. This approach will enable an interpretation of the contribution of dairy fat in protecting against PPH-induced VED while providing findings to fill this research knowledge gap.

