Trial 1: A separate cohort of participants will visit our study center for Objective 3. On the morning of testing, subjects will arrive at the laboratory after abstaining from food and beverage except water for 10-12 hours. Height, weight and two blood pressure measurements will be obtained using standard procedures. A finger prick will be performed to measure baseline HbA1c and a flexible catheter will be inserted into a forearm vein. After a 15 min supine stabilization period, a blood sample will be obtained from a 3-way stopcock connected to the end of the catheter. Blood will be collected with a syringe and transferred to appropriate tubes for processing and subsequent determination of fasting biochemical measurements. We will then perform fasting measurements of flow-mediated dilation (FMD) and carotid intima media thickness (cIMT) using ultrasound (described below). Following these baseline measurements, participants will ingest 75 g glucose dissolved in water. FMD measurements will be performed intermittently post-ingestion at 30, 60, 90, 120, 150, and 180 minutes. Blood samples will be collected at 0 min (immediately prior to eating) and at 30, 60, 90, 120, 150, and 180 minutes following the ingestion of the beverage. After each blood sample is obtained, the catheter will be flushed with saline in order to prevent the formation of clots and to minimize the likelihood of having to insert a needle again. Subjects will remain supine in a comfortable position for the entire duration of the test. A trained phlebotomist will perform all cannula insertions, needle sticks, and blood collections.

Trial 2: Participants will visit our study center again, and will complete the procedure as described above (Trial 1) with the exception that they will ingest glucose (75 g) dissolved in non-fat milk.

Trial 3: Participants will visit our study center again, and will complete the procedure as described above (Trial 1) with the exception that they will ingest glucose (75 g) dissolved in whole milk.

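### The same glucose versus glucose-plus-non-fat-milk contrast is run in both studies, but no combined estimate is planned: a missed gain in precision, mainly for plasma markers that were never sized

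*Combined protocol and SAP*

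**What the plan says.** Study Design sets out two randomised cross-over studies: "Each study aims to enroll 24 participants for a total of 48 participants for all of the anticipated work". Study 1 has four arms and serves Objectives 1 and 2. Study 2 has three arms, serves Objective 3, and "will utilize a different cohort of participants".

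The two studies share a pair of drinks. For Objective 1, participants "in the fasted state will ingest 75 g glucose dissolved in water or nonfat milk (2 cups; 473 mL) on two occasions". For Objective 3, the other cohort takes part by "ingesting glucose (75 g), or glucose with non-fat milk or whole milk (2 cups; 473 mL) on three occasions". In the trial descriptions, Trial 1 is glucose in water in both studies, and Trial 2 is worded the same way in both: "they will ingest glucose (75 g) dissolved in non-fat milk". On measurements, Study Design says for Objective 3: "Identical to Objectives 1-2, FMD and blood samples will be obtained at 30 min intervals for 3 h". Entry criteria, washout, dietary control and measurement methods are written once, for both studies.

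Power Calculation and Statistics then states that "statistical analysis will be handled discretely to examine differences between trials within each" Objective. AUCs are compared by a paired t-test for Objectives 1-2 and by a 1-way ANOVA for Objective 3. Data Analysis repeats these tests. Neither section mentions an estimate that uses both cohorts.

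**The concern.** The effect of non-fat milk on the response to a glucose load is measured within person in 48 people, yet every planned estimate of it uses 24. The two cohorts differ by design only in the other drinks they receive, so few pairs of studies are better suited to a combined estimate.

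What is at stake is precision. The sample size rests on FMD alone, whereas the central hypothesis is mechanistic and depends on plasma markers of oxidative stress and nitric oxide status. No effect size, SD or power is given for any of these. Wide intervals are most likely there, and the design already collects the data that would narrow them. Without a prespecified analysis, any later pooling would be a choice made after the results were known. It would also have to bridge two different AUC tests for the same contrast.

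**Working it through.** **Inputs.** 24 participants per study, 48 in all (Study Design). 80% power with 11 people at P<0.05, and more than 90% with 24 (Power Calculation and Statistics). Sidedness is not stated; I take two-sided. No effect size or SD is given, so results are in units of the SD of the paired difference, and dz is the mean paired difference divided by that SD. The water volume is written out for Objective 1 only (473 mL, Justification of Test Meals); I take it to be the same in Study 2.

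**1. The plan's own figure.** Without an effect size, n = 11 cannot be derived independently. Solving the paired t-test (noncentral t) backwards from n = 11 and 80% power gives dz = 0.938. At that effect, power with 24 is 99.3%; it is 96% with 18 completers and 90% with 14. A one-sided test gives dz = 0.806 and 98.6% power at 24. The plan's claim of more than 90% is consistent with its n = 11.

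**2. Standard error.** The SE of the mean paired difference is SD/√n.
- n = 24: 1/√24 = 0.204 SD
- n = 48: 1/√48 = 0.144 SD
- ratio 0.707, a reduction of 29%

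**3. 95% confidence interval half-width,** t × SE, with 23 df for one study and 46 df for two cohorts stratified by study.
- n = 24: 2.069 × 0.2041 = 0.42 SD
- n = 48: 2.013 × 0.1443 = 0.29 SD

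With 18 completers in each study, the figures are 2.110/√18 = 0.50 and 2.032/√36 = 0.34 SD. The relative gain is about the same.

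**4. Power, two-sided 5%.** The first two rows are my illustrative values for an unsized marker; the last three are fractions of the back-solved FMD effect.

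| dz | n = 24 | n = 48 |
|---|---|---|
| 0.40 | 47% | 77% |
| 0.50 | 65% | 92% |
| 0.469 (half the FMD effect) | 60% | 89% |
| 0.703 (three quarters) | 91% | 99.8% |
| 0.938 (FMD planning effect) | 99.3% | >99.9% |

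The dz detectable with 80% power falls from 0.60 to 0.41.

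**5. Which outcomes were not sized.** Sample Handling lists glucose, insulin, triglyceride, total cholesterol, nitrite/nitrate, arginine, ADMA, BH₄, BH₂, endothelin-1, 11-dehydro-TXB₂, malondialdehyde and methylglyoxal. That is 13, counting nitrite/nitrate as one and leaving out vitamins C and E, which are baseline measures only.

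**6. Chance that one study is significant and the other is not,** p₁(1 − p₂) + p₂(1 − p₁), for the same true effect in both.
- Planning effect, 0.05 in both: 2 × 0.9925 × 0.0075 = 1.5%.
- Planning effect, Bonferroni 0.05/3 in Study 2: 0.9925 × 0.0284 + 0.9716 × 0.0075 = 3.5%.
- Half that effect: 48% and 52%.

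These treat the Study 2 comparison as a paired t-test and ignore the overall ANOVA that precedes it.

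**7. What a consistency check can show.** The SE of the difference between the two studies' effects is √(2/24) = 0.289 SD, so its 95% half-width is 2.013 × 0.289 = 0.58 SD. It has 80% power only for a between-study difference of about 0.83 SD.

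**The case against.** The strongest reply is that nothing here is wrong. Study 2 was designed and sized separately, for a different question. Justification of Test Meals gives its purpose: "This approach will enable an interpretation of the contribution of dairy fat in protecting against PPH-induced VED". Non-fat milk is there as the within-person comparator for whole milk. Two self-contained studies, the second giving an independent replication of the milk contrast, are a legitimate design. The sentence on separate analysis chiefly explains why Study 1's four arms are split between Objectives 1 and 2; it is not a decision against combining cohorts. For FMD, pooling adds less than one percentage point of power at the implied effect. For the markers, no effect or SD is given, so the benefit in power is not known.

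All of this stands, and it rules out three stronger inferences. A reader might infer that Objective 1 is answered with half its data. The documents assign Objective 1 to Study 1, so the Study 2 arms are extra evidence, not discarded Objective 1 data. A reader might infer that Objective 1 is underpowered; for FMD, on the plan's own figures, it is not. A reader might also infer that one significant and one non-significant result would leave Objective 1 without an answer. Study 1 would still give it, and two such results can come from fully compatible estimates.

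The reply does not remove the precision gain, which follows from the number of people whatever the marker's effect size. Nor does the plan describe the repeated contrast as a replication or say how it will be read.

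**Conclusion.** The point holds as a cheap improvement, not as a fault in the sample size or in the planned tests. The repeated contrast and the absence of any combined estimate are plain from the text. A combined estimate would have a 29% smaller standard error, provided that the SD of the paired difference is similar in the two cohorts and that completion is full, or at least similar. The gain matters little for FMD at the implied effect and most for the unsized markers. How much power it buys for any one marker cannot be stated from the documents; the values of 0.4 and 0.5 only show the range in which it would be material. The FMD figures rest on an effect back-solved from n = 11.

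Making the pooled estimate the primary answer to Objective 1 is a step the documents do not require. It would make a self-contained study wait for another and give up the independent replication.

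**What to change.** Keep Study 1 as the primary analysis for Objective 1, and say so. Add to Power Calculation and Statistics and to Data Analysis a prespecified secondary analysis:

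- Estimate the difference between glucose in water and glucose in non-fat milk, for FMD and for the AUC of each postprandial marker, from both cohorts together, within participant and stratified by study.
- Use the same paired contrast in both cohorts for this purpose, whatever test each Objective uses.
- Show each study's estimate and confidence interval beside the pooled one.
- Report the study-by-drink interaction with its confidence interval as a descriptive check, and state that it has low power, so that a non-significant result is not read as proof of consistency.

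The text should be added before the codes are broken. The cost is one more analysis, with no new participants, samples or visits. The pooled estimate is available only once Study 2 is complete; the Study 1 report need not wait for it.

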Test Trials. Each participant in studies under Objectives 1 and 2 will complete a 4-arm, randomized, cross-over study. On 4 occasions separated by ≥ 7 d for men and 1 mo for women (women require vascular testing at the same time during their menstrual cycle to account for known changes in vascular reactivity), participants will report in the fasted state (10-12 hours) to the study center. In Objective 1, participants will ingest 75 g glucose dissolved in water or non-fat milk (2 cups; 473 mL). In Objective 2, participants will ingest 75 g glucose with isonitrogenous quantities of whey protein isolate of sodium caseinate (16.5 g in 473 mL water). In Objective 3, a separate cohort of men and women will complete a 3-arm, randomized, cross-over study. On 3 occasions separated by intervals identical to those in Objectives 1 and 2, participants will ingest 75 g glucose alone or 75 g glucose dissolved in non-fat milk or whole milk (2 cups; 473 mL). This volume of milk was chosen to be consistent with our work and recommendations of the US Dietary Guidelines for Americans. For Objective 2, protein is being administered at 16.5 g to reflect total protein of non-fat milk, rather than their proportional contributions in milk. The amount of glucose included in each mixed beverage (75 g) is equivalent to the dose of a clinical oral glucose challenge, which we and others have routinely shown to induce PPH, oxidative stress, and VED. Then, at 30 minute intervals during the 3 hour postprandial period, we will assess brachial artery flow-mediated dilation (FMD) via non-invasive ultrasonography and blood biomarkers. To ensure that the order by which each participant completes each trial is randomized, a random sequence generator (<http://www.random.org/sequences/>) will be used to determine the order by which each participant will undergo the respective trials. While the trials will be conducted in a randomized order, for simplicity, they have been listed as Trials 1 – 4 below for Objectives 1 and 2 and Trials 1 – 3 below for Objective 3. Because participants will be consuming moderate volumes of fluid, they will have access to use the restroom as needed in-between collection points.

Objectives 1 and 2

The 4-arm, randomized, cross-over study under these objectives will be completed by a separate cohort of prediabetic men and women from those described under Objective 3.

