Trial 1: On the morning of testing, subjects will arrive at the laboratory after abstaining from food for 10-12 hours. Height, weight and two blood pressure measurements will be obtained using standard procedures. A finger prick will be performed to measure baseline hemoglobinA1c (HbA1c) and a flexible catheter will be inserted into a forearm vein. After a 15 min supine stabilization period, a blood sample will be obtained from a 3-way stopcock connected to the end of the catheter. Blood will be collected with a syringe and transferred to appropriate tubes for processing and subsequent determination of fasting biochemical measurements. We will then perform fasting measurements of flow-mediated dilation (FMD) and carotid intima media thickness (cIMT) using ultrasound (described below). Following these baseline measurements, participants will ingest 75 g glucose dissolved in water. FMD measurements will be performed intermittently post-ingestion at 30, 60, 90, 120, 150, and 180 minutes. Blood samples will be collected at 0 min (immediately prior to eating) and at 30, 60, 90, 120, 150, and 180 minutes following the ingestion of the beverage. After each blood sample is obtained, the catheter will be flushed with saline in order to prevent the formation of clots and to minimize the likelihood of having to insert a needle again. Subjects will remain supine in a comfortable position for the entire duration of the test. A trained phlebotomist will perform all cannula insertions, needle sticks, and blood collections.

Trial 2: Participants will visit our study center again, and will complete the procedure as described above (Trial 1) with the exception that they will ingest glucose (75 g) dissolved in non-fat milk.

Trial 3: Participants will visit our study center again, and will complete the procedure as described above (Trial 1) with the exception that they will ingest glucose (75 g) with isonitrogenous quantities of whey protein isolate (16.5 g in 473 mL water).

Trial 4: Participants will visit our study center again, and will complete the procedure as described above (Trial 1) with the exception that they will ingest glucose (75 g) with isonitrogenous quantities of sodium caseinate (16.5 g in 473 mL water).

Objective 3

The 3-arm, randomized, cross-over study under this objective will be completed by a separate cohort of prediabetic men and women from those described under Objectives 1 and 2.

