Brachial Artery Flow-Mediated Dilation (FMD). FMD will be measured to assess vascular endothelial function as a functional index of the impact of each beverage's ingestion on arterial blood flow. In brief, FMD is determined by a blinded, trained research assistant using an Acuson 13 MHz linear array transducer and a cardiac ultrasound system. Echocardiogram (ECG) is used to monitor heart rate throughout the procedure. Prior to testing, the participant is resting in the supine position for 10 min. Using ultrasound, the brachial artery will be located and the transducer will be secured in place to ensure consistent image acquisition. FMD measurements will be conducted by placing an inflatable cuff just below the antecubital fossa (crease of the elbow). The procedure is initiated by obtaining resting images (30 sec) of the brachial artery, followed by arterial occlusion (5 min) using the aforementioned inflatable cuff. The cuff is then rapidly deflated and post-occlusion ultrasound images are collected for 300 heart beats, which are analyzed using semi-automated software to calculate the ECG-gated measurement of dilation responses. Post-occlusion vessel diameters at 1 and 3 min, and peak diameter, will be used to calculate percent dilation relative to the pre-occlusion diameter. Post-occlusion peak blood flow velocity will also be collected simultaneously to normalize FMD responses to shear-stress (i.e. post-occlusion blood flow).

Carotid Intima Media Thickness (cIMT). cIMT will be measured at baseline of each trial to assess vascular endothelial function. While anticipated to be unchanged during the study, its assessment will allow for its consideration as a statistical co-variate in defining physiologic responses to test beverages. Images of the right- and left-sided far wall of the common carotid artery will be recorded for ~10 heartbeats and analyzed using edge-detection software to obtain mean, maximum, and minimum lumen diameter, and cIMT. Plaque

is defined by the presence of focal wall thickening that is $\geq 50\%$ greater than that of the surrounding vessel wall or ≥ 1.5 mm cIMT protrusion that is distinct from the adjacent boundary.

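### The 0-min value is measured at every trial but is not a covariate in the AUC0-3h comparison; the between-trial baseline test cannot replace adjustment, so precision is lost

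*Combined protocol and SAP*

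**What the plan says.** All places are in section III of the combined protocol and SAP.

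- **Collection.** Under Objectives 1 and 2, Trial 1, before the drink: "We will then perform fasting measurements of flow-mediated dilation (FMD) and carotid intima media thickness (cIMT) using ultrasound". The Objective 3 trial has the same schedule: "Blood samples will be collected at 0 min (immediately prior to eating) and at 30, 60, 90, 120, 150, and 180 minutes". Measurement / Instrumentation confirms that biomarkers and functional vascular indices share the 0-min and half-hourly schedule unless otherwise noted.
- **Baseline test.** Power Calculation and Statistics, repeated in Data Analysis, gives a paired t-test for Objectives 1-2 or "1-way RM ANOVA (*Objective 3*) to ensure no changes in participant health status". Neither place says what follows a significant result.
- **Main model.** "Other analyses will be performed by 2-way RM ANOVA to define time and treatment effects, and their interaction". No covariate is named.
- **AUC0-3h.** It is meant to make comparisons more sensitive and to "simplify analyses to a paired t-test (*Objectives 1-2*) or 1-way ANOVA (*Objective 3*) as we described". Again no covariate is named. The text does not say whether AUC is total or incremental, and it refers to earlier papers. AUC is promised for biomarkers, which Measurement / Instrumentation lists separately from functional indices, so whether FMD gets an AUC is not explicit.
- **Only covariate mentioned.** For carotid intima media thickness, "its assessment will allow for its consideration as a statistical co-variate in defining physiologic responses to test beverages". It is expected not to change during the study.
- **Order of trials.** Under Test Trials, a random sequence generator "will be used to determine the order by which each participant will undergo the respective trials".

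**The concern.** A non-significant baseline test is weak evidence that trial days were comparable, and with no true shift a 5% test still flags 5% of variables. Neither result changes the analysis. The 0-min value, which could correct for day-to-day differences, is left out of the AUC comparison as a covariate. Carotid thickness cannot do this job: a value that stays constant within a person cancels from a within-person drink contrast. FMD expressed as a percentage does not do it either, because each reading is scaled to its own pre-occlusion diameter and not to that day's 0-min FMD.

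At stake is precision, most of all for contrasts that the sample-size statement does not cover (whey versus casein, whole versus non-fat milk) and for secondary biomarkers.

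**Working it through.** **1. The plan's own figure.** The power statement gives 11 participants for 80% power at P<0.05 and more than 90% with 24. It says the team "predicted that non-fat milk will protect against PPH-mediated decreases in FMD" but gives no effect or SD, so 11 cannot be reproduced directly. Solving the two-sided paired t-test (noncentral t) for 80% at n = 11 gives a standardised paired effect dz = 0.938. At n = 24 the power is then 99%, which is consistent with the statement.

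**2. The baseline test.** Power uses noncentral t with 23 df and noncentrality d√24, where d is the shift in SDs of the paired difference. It is 29% at d = 0.3, 47% at 0.4, 65% at 0.5, 80% at 0.6 and 99% at 0.94. The 95% CI half-width is 2.069/√24 = 0.42 SD.

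**3. Weight of the pre-drink value.** Trapezoid weights at 0, 30, ..., 180 min are 0.25, 0.5 (five times) and 0.25 h, which sum to 3 h. The 0-min value carries 0.25/3 = 1/12 of total AUC. It carries 1/7 of the treatment main effect if 0 min is one of seven time levels, so a constant effect from 30 min onward is diluted to 6/7.

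**4. Gain from adjustment.** The documents give no SDs or correlations, so the inputs are assumed. Let rho be the correlation between time points of the between-drink paired difference, with unit variance. It is either equal for all pairs or lag-one under AR(1). For equal correlation:

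- Var(AUC) = 1.375(1 − rho) + 9 rho
- Cov(AUC, 0 min) = 0.25 + 2.75 rho
- r² = Cov²/Var(AUC)
- adjusted/total = (1 − r²)(1 + 1/(n − 3))
- net incremental variance = Var(AUC) − 6 Cov + 9

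Worked at rho 0.33 and n = 24: Var = 0.921 + 2.970 = 3.891; Cov = 1.158; r² = 0.344; adjusted/total = 0.656 × 1.048 = 0.69. Incremental/total = (3.891 − 6.945 + 9)/3.891 = 1.53, so adjusted/incremental = 0.69/1.53 = 0.45.

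| Variance ratio | rho 0 | 0.1 | 0.2 | 0.33 | 0.5 | 0.67 |
|---|---|---|---|---|---|---|
| Adjusted/total, n = 24, equal | 1.00 | 0.91 | 0.82 | 0.69 | 0.51 | 0.34 |
| Adjusted/total, n = 24, AR(1) | 1.00 | 0.99 | 0.97 | 0.94 | 0.88 | 0.75 |
| Adjusted/total, n = 15, equal | 1.03 | 0.94 | 0.84 | 0.71 | 0.53 | 0.35 |
| Adjusted/total, n = 15, AR(1) | 1.03 | 1.02 | 1.01 | 0.98 | 0.91 | 0.78 |
| Adjusted/net incremental, n = 24, equal | 0.15 | 0.24 | 0.33 | 0.45 | 0.60 | 0.75 |
| Adjusted/net incremental, n = 24, AR(1) | 0.15 | 0.18 | 0.22 | 0.28 | 0.37 | 0.52 |

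Against the seven-time main effect, for a constant post-drink effect, the ratio runs from 0.94 to 0.30 (equal) or 0.94 to 0.70 (AR(1)). For Objective 3 (three drinks, within-person slope, n = 24), adjusted/total runs from 0.98 to 0.34 or 0.98 to 0.73.

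**5. Total or incremental.** The net incremental difference is the total difference minus 3 times the 0-min difference. Regressed on the 0-min difference, the slope falls by 3 and the intercept is unchanged. Both versions therefore give the same treatment estimate.

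**6. Power illustration.** Take dz = 0.938/2 = 0.469, an assumed value. Unadjusted power at n = 24 is 0.595. Adjusted power (22 df) runs from 0.593 at rho 0 to 0.964 (equal) or 0.717 (AR(1)) at rho 0.67.

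**7. Error rates.** In simulation (20,000 trials per cell) overall type I error was 0.047-0.051 for total, incremental and adjusted AUC. Now condition on a chance baseline difference of k = 1.9 standard errors, which the planned test would miss. By normal approximation the unadjusted error is 1 − Φ((1.96 − rk)/√(1 − r²)) + Φ((−1.96 − rk)/√(1 − r²)). For an assumed correlation r between the 0-min and outcome differences of 0.3, 0.5 and 0.7, this is 7.7%, 12% and 19%.

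**The case against.** The strongest reply is that nothing here is invalid: an unadjusted paired comparison in a randomised crossover holds its error rate. That stands.

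The size of the gain rests wholly on an assumed rho. That also stands. Fasting, replicated diets, cycle timing and a single FMD technician may keep rho low. Under AR(1) with rho up to 0.33, adjustment saves at most 6% of the variance of total AUC, and the 0.595 power in the illustration rises only to 0.618.

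The AUC type may be defined in the cited papers. That is fair: it is not visible in this document, which differs from being undecided. If it is net incremental, the 0-min value is already subtracted, but with a fixed slope. At rho 0 that gives 6.45 times the variance of total AUC.

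The baseline test is aimed at health status, for which HbA1c, insulin resistance and vitamins E and C are also measured, and it is not offered as a substitute for adjustment. This stands in part; the claim to ensure no change is still more than the test can deliver.

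A reader might infer that the plan ignores baseline altogether. It does not: if 0 min is a time level, which is the natural reading, the time-by-treatment interaction already reflects change from baseline.

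**Conclusion.** The point holds as a worthwhile, inexpensive improvement. No 0-min covariate is named for AUC0-3h, the main effect averages in a pre-drink value if 0 min is a time level, and the baseline test neither shows comparability nor leads to any action. The variance saving is 0-66% (equal) or 0-25% (AR(1)) if the planned AUC is total, and 25-85% or 48-85% if it is net incremental, for assumed rho of 0 to 0.67. Confidence in the size is medium, because the documents give no correlation.

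Two stronger readings are not supported. One is that the results would be biased or the type I error inflated: order is randomised and overall error stays near 5%. The conditional figures above describe unlucky samples, not the procedure as a whole. The other is that the trial is underpowered: non-fat milk versus glucose on FMD has about 99% power at the effect implied by n = 11. A results-driven choice of AUC is also limited, since Internal Validity keeps the codes unbroken until the analysis is verified.

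**What to change.** Amend Power Calculation and Statistics and Data Analysis:

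1. Report 0-min values by trial descriptively, and do not use the significance test to claim comparability.
2. Make the baseline-adjusted AUC0-3h comparison the overall treatment test, in place of the RM ANOVA treatment main effect. For Objectives 1-2, regress the paired AUC difference on the paired 0-min difference; the intercept is the treatment effect. For Objective 3, fit a mixed model with participant random and with trial-day 0-min and participant-mean 0-min values as covariates, followed by Bonferroni contrasts.
3. Keep the 2-way RM ANOVA, with 0 min stated as a time level, for time and time-by-treatment effects only.
4. State the AUC type and that FMD is included. Total and net incremental AUC then agree on the treatment estimate; a positive-only incremental AUC would not.

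The cost is wording and one or two degrees of freedom, with no new data. If rho is near 0, the loss against total AUC at n = 24 is trivial (power 0.593 versus 0.595). With an assumed 15 completers it is about 3% more variance. Judged on 95% CI width with 15 completers, adjustment breaks even at rho of about 0.06 (equal) or 0.30 (AR(1)).
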